### **Preexisting Condition**

A preexisting condition is one that is present at the start of the study. A preexisting condition should be recorded as an adverse event if the frequency, intensity, or the character of the condition worsens during the study period.

### **General Physical Examination Findings**

At screening, any clinically significant abnormality should be recorded as a preexisting condition. At the end of the study, any new clinically significant findings/abnormalities that meet the definition of an adverse event must also be recorded and documented as an adverse event.

### **Post-study Adverse Event**

All unresolved adverse events should be followed by the investigator until the events are resolved, the subject is lost to follow-up, or the adverse event is otherwise explained. At the last scheduled visit, the

investigator should instruct each subject to report any subsequent event(s) that the subject, or the subject's personal physician, believes might reasonably be related to participation in this study. The investigator should notify the study sponsor of any death or adverse event occurring at any time after a subject has discontinued or terminated study participation that may reasonably be related to this study. The sponsor should also be notified if the investigator should become aware of the development of cancer or of a congenital anomaly in a subsequently conceived offspring of a subject that has participated in this study.

### **Abnormal Laboratory Values**

A clinical laboratory abnormality should be documented as an adverse event if any one of the following conditions is met:

- The laboratory abnormality is not otherwise refuted by a repeat test to confirm the abnormality
- The abnormality suggests a disease and/or organ toxicity
- The abnormality is of a degree that requires active management; e.g. change of dose, discontinuation of the drug, more frequent follow-up assessments, further diagnostic investigation, etc.

### **Hospitalization, Prolonged Hospitalization or Surgery**

Any adverse event that results in hospitalization or prolonged hospitalization should be documented and reported as a serious adverse event unless specifically instructed otherwise in this protocol. Any condition responsible for surgery should be documented as an adverse event if the condition meets the criteria for an adverse event.

Neither the condition, hospitalization, prolonged hospitalization, nor surgery are reported as an adverse event in the following circumstances:

- Hospitalization or prolonged hospitalization for diagnostic or elective surgical procedures for a preexisting condition. Surgery should **not** be reported as an outcome of an adverse event if the purpose of the surgery was elective or diagnostic and the outcome was uneventful.
- Hospitalization or prolonged hospitalization required to allow efficacy measurement for the study.
- Hospitalization or prolonged hospitalization for therapy of the target disease of the study, unless it is a worsening or increase in frequency of hospital admissions as judged by the clinical investigator.

## **7.2 Recording of Adverse Events**

At each contact with the subject, the investigator must seek information on adverse events by specific questioning and, as appropriate, by examination. Information on all adverse events should be recorded immediately in the source document, and also in the appropriate adverse event module of the case report form (CRF). All clearly related signs, symptoms, and abnormal diagnostic procedures results should be recorded in the source document, though should be grouped under one diagnosis.

All adverse events occurring during the study period must be recorded. The clinical course of each event should be followed until resolution, stabilization, or until it has been determined that the study treatment or participation is not the cause. Serious adverse events that are still ongoing at the end of the study period must be followed up to determine the final outcome. Any serious adverse event that occurs after the study period and is considered to be possibly related to the study treatment or study participation should be recorded and reported immediately.

## **7.3 Reporting of Serious Adverse Events and Unanticipated Problems**

Investigators and the protocol sponsor will conform to the adverse event reporting timelines, formats and requirements of the various entities to which they are responsible, but at a minimum those events that must be reported are those that are:

- related to study participation,
- unexpected, and
- serious or involve risks to subjects or others  
(see definitions, section 8.1).

If the report is supplied as a narrative, the minimum necessary information to be provided at the time of the initial report includes:

- Study identifier
- Study Center
- Subject number
- A description of the event
- Date of onset
- Current status
- Whether study treatment was discontinued
- The reason why the event is classified as serious
- Investigator assessment of the association between the event and study treatment

### **7.3.1 Investigator reporting: notifying the study sponsor**

Any study-related unanticipated problem posing risk of harm to subjects or others, and any type of serious adverse event, must be reported to the study sponsor by telephone within 24 hours of the event. To report such events, a Serious Adverse Event (SAE) form must be completed by the investigator and faxed to the study sponsor within 24 hours. The investigator will keep a copy of this SAE form on file at the study site.

Within the following 48 hours, the investigator must provide further information on the serious adverse event or the unanticipated problem in the form of a written narrative. This should include a copy of the completed Serious Adverse Event form, and any other diagnostic information that will assist the understanding of the event. Significant new information on ongoing serious adverse events should be provided promptly to the study sponsor.

### **7.3.2 Investigator reporting:**

For reportable deaths, the initial submission to the UNC IRB may be made by contacting the IRB Director or Associate Director. The AE/Unanticipated Problem Form is required as a follow up to the initial submission.

#### **Other Reportable events:**

For clinical drug trials, the following events are also reportable to the UNC IRB:

- Any adverse experience that, even without detailed analysis, represents a serious unexpected adverse event that is rare in the absence of drug exposure (such as agranulocytosis, hepatic necrosis, Stevens-Johnson syndrome).
- Any adverse event that would cause the sponsor to modify the investigators brochure, protocol or informed consent form, or would prompt other action by the IRB to assure protection of human subjects.
- Information that indicates a change to the risks or potential benefits of the research, in terms of severity or frequency. For example:
  - An interim analysis indicates that participants have a lower rate of response to treatment than initially expected.
  - Safety monitoring indicates that a particular side effect is more severe, or more frequent than initially expected.
  - A paper is published from another study that shows that an arm of your research study is of no therapeutic value.
- Change in FDA safety labeling or withdrawal from marketing of a drug, device, or biologic used in a research protocol.
- Breach of confidentiality
- Change to the protocol taken without prior IRB review to eliminate apparent immediate hazard to a research participant.
- Incarceration of a participant when the research was not previously approved under Subpart C and the investigator believes it is in the best interest of the subject to remain on the study.
- Complaint of a participant when the complaint indicates unexpected risks or the complaint cannot be resolved by the research team.

- Protocol violation (meaning an accidental or unintentional deviation from the IRB approved protocol) that in the opinion of the investigator placed one or more participants at increased risk, or affects the rights or welfare of subjects.

### **7.3.3 Investigator reporting:**

Investigators who are not UNC faculty or affiliated with a UNC research site are responsible for safety reporting to their local IRB. Investigators are responsible for complying with their local IRB's reporting requirements, though must submit the required reports to their IRB no later than 10 working days. Copies of each report and documentation of IRB notification and receipt will be kept in the investigator's study file.

### **7.3.4 Sponsor reporting: Notifying the FDA**

The study PI will report certain study events in an expedited fashion to the FDA. These written notifications of adverse events are referred to as IND safety reports. The following describes the safety reporting requirements by timeline for reporting and associated type of event:

- ***Within 7 calendar days***

Any study event that is:

- associated with the use of the study drug
- unexpected,
- fatal or life-threatening, and

- ***Within 15 calendar days***

Any study event that is:

- associated with the use of the study drug,
- unexpected, and
- serious, but not fatal or life-threatening

-or-

- a previous adverse event that was not initially deemed reportable but is later found to fit the criteria for reporting (reporting within 15 calendar days from when event was deemed reportable).

Any finding from tests in laboratory animals that:

- suggest a significant risk for human subjects including reports of mutagenicity, teratogenicity, or carcinogenicity.

#### **Additional reporting requirements**

Sponsors are also required to identify in IND safety reports all previous reports concerning similar adverse events and to analyze the significance of the current event in light of the previous reports.

#### **Reporting Process**

Adverse events may be submitted on FDA Form 3500A or in a narrative format. If supplied as in a narrative format, the minimum information to be supplied is noted above at the beginning of section 8.3.

### **7.3.5 Sponsor reporting: Notifying participating investigators**

It is the responsibility of the study sponsor to notify all participating investigators, in a written IND safety report, of any adverse event associated with the use of the drug that is both serious and unexpected, as well as any finding from tests in laboratory animals that suggest a significant risk for human subjects. Additionally, sponsors are also required to identify in IND safety reports all previous reports concerning similar adverse events and to analyze the significance of the current event in light of the previous reports.

### **7.4 Unblinding Procedures**

Unblinding the group in which the patient is randomized will only occur in exceptional circumstances when the knowledge of treatment is essential for the management of an individual patient. In emergency situations (e.g. anaphylaxis) the principal investigator may contact IDS to have the identity of the patient's treatment drug revealed to help manage the patient more effectively. If this occurs, the unblinding procedure will be documented in the patient's source documents. If emergency unblinding is needed, it will likely occur in the context of a serious adverse event and will be reported to the FDA along with the SAE. Unblinding will be reported similar to an SAE within 24 hours by phone or fax, followed by a written narrative of the event within 48 hours.

### 7.5 Stopping Rules

The entire trial will stop if any investigator judges it necessary for medical, safety, regulatory, or other reasons consistent with applicable laws, regulations, or good clinical practice.

### 7.6 Medical Monitoring

**A. Safety Monitoring Plan:** Overall safety oversight will be the responsibility of the data coordinating center PI (DCC PI). Monitoring the study (across one or more study sites) is considerably facilitated by the use of a single electronic database

which can be reviewed by the network PI, study site PI(s), and other investigators. The DCC PI will monitor for adverse events that change study risk level and this will be communicated with the independent medical monitor if needed. Adverse events at individual study sites will also be monitored by the site PI. If an

Serious AE	Death Life threatening reaction Inpatient hospitalization prolonged, or rehospitalization Persistent or significant disability/incapacity Congenital anomaly/birth defect Represents other significant hazards or potentially serious harm to research subjects (similar to "important medical event")
Expected AE	Known potential effect of the drug (based on drug description information from manufacturer) or disease process

adverse event occurs which changes the study risk level, the DCC PI will immediately report this event to the DCC IRB (UNC IRB), inform the site PI(s), and oversee the process of modifying the study at the study site(s) as appropriate to address the change in risk. The DCC PI will also provide annual reports summarizing AE data to the data coordinating center IRB (UNC IRB) and any other requesting IRB. The site PI(s) will oversee patient safety at their site, with delegation of responsibilities to other investigators and designated study personnel as appropriate. The DCC PI, together with their study site teams, will ensure that all entry criteria are met prior to the initiation of the protocol, and that all study procedures and reporting of adverse events are performed according to the protocol. Serious adverse events (SAE's) will be monitored by the study site investigative teams in real time throughout the trial.

**Patient monitoring:** An adverse event is any physical or clinical change experienced by the patient. This includes the onset of new symptoms and the exacerbation of pre-existing conditions. Adverse event assessments will be performed according to the following schedule:

**Adverse event monitoring after discharge:** Adverse events will be assessed at each patient contact (telephone or text-messaged/mailed survey), which will occur weekly while on the study drug.

**Additional reporting:** In addition to receiving these regular side effect assessments, patients will be given a toll free study number to reach the study team at the DCC, as well as telephone/pager numbers for individuals at the study site, and will be instructed to call these numbers if they experience any changes in their health status or if they have questions regarding the study medication.

Category definitions for adverse events are shown in Table 7. An electronic adverse event form will be completed for all unanticipated AEs. The severity of the AE will be assessed a CTCAE grade will be recorded for each. An investigator will also assess the relationship of any adverse event to study medication or procedures. Severity assessments will be performed using the Common Toxicity Criteria (<http://ctep.cancer.gov/>). The time table for reporting serious and other adverse events is shown in Table 7.

*Unanticipated problems involving risks to participants or others, defined as any incident, experience or outcome that is both*

**Table 7.** Time table for reporting unanticipated adverse events.

Unanticipated	
Serious AE	One week
Not Serious AE/other	Two weeks

unexpected and related or possibly related to the research, will be reported to the IRB. Unanticipated problems that are serious adverse events will be reported to the IRB within 1 week of the investigator becoming aware of the event. Any other unanticipated problem will be reported to the IRB within 2 weeks of the investigator becoming aware of the problem. The study team will report all serious unanticipated adverse events to the DCC PI immediately, and will review all non-serious unanticipated adverse events with the PI within 24 hours.

Patients with adverse events will be monitored with relevant clinical assessments (and laboratory tests if necessary) as determined by an investigator in collaboration with the patient's care team. All adverse events will be followed to satisfactory resolution or stabilization of the event(s). Any actions taken and follow-up results will be recorded on the appropriate AE form and given a CTCAE grade.

Appendix 2 describes the adverse event grading scale and management guidelines for potential adverse events related to the study drugs. This chart covers a number of common adverse effects, but will not be comprehensive. As other situations are encountered and managed by the study team, this decision rule chart will be updated and expanded so that it remains current and inclusive.

Summary information regarding adverse events will be provided to the IRB at the time of annual IRB renewal. As described below, medical monitor reports will also be submitted to the UNC IRB on a quarterly basis. Criteria for stopping the study trial among all participants for review are shown in Appendix 2.

Patients experiencing adverse effects that in the opinion of the investigators merit drug dosage adjustment will have their dosage advanced more slowly, or the next dose reduced or held as appropriate. If necessary, patients will be maintained on a lower dose, or their dose will be re-advanced depending on the nature of the side effect(s). Patients who decline further participation and patients experiencing adverse effects that in the opinion of study investigators indicate that study drug should be stopped will be discontinued or tapered from study medication.

**Independent Medical Monitor:** To handle individual problems that may require communication directly with physician caring for the patient, or if decision making involves altering the study drug administration on a patient level, an independent Medical Monitor will become involved. This is to avoid any conflicts of interest that may arise. Data Handling and Record Keeping

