## **5 Study Procedures**

### **5.1 Enrollment Procedures**

This first visit will take place upon admission to the hospital following a major thermal burn injury within 72 hours of MThBI. Patients enrolled in the study will be randomized (1. once consents are signed and 2. baseline data is collected) into a 2x2 factorial design with 1:1:1:1 allocation as described in the study

overview. Burn survivors qualifying for this study are generally hospitalized for a period of time (typically 7-14 days) and therefore will start the study drug immediately after enrollment questionnaire has been completed and continue daily dosing during their stay. Upon discharge of the patient a supply sufficient to complete a 6 week course of study drugs will be dispensed by study staff.

Medical record information abstracted at time of admission will include information related to patient past medical history and initial burn care, and medication use prior to admission and prior to enrollment. Laboratory values relevant to patient renal and hepatic function will also be obtained, along with any toxicology labs obtained by the primary treating team.

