## **5.3 Data Extraction**

Medical record information abstracted after discharge will include information on the patient's health status and care during hospitalization and at the time of discharge. This information will include burn characteristics (e.g. TBSA, depth, location, mechanism), medications taken during admission, and discharge medications. Data collected regarding the surgical procedure will include donor site location, size, mesh ratio, mechanism of grafting (e.g., staples or fibrin glue), location of grafting, and date of surgery.

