## **5.4 Text messaged or e-mailed outpatient Weekly Pain and Compliance Assessments**

Brief, weekly assessments of number of missed doses in the past week and graft site pain severity (0-10 NRS) over the past 24 hours will occur via automated text message/e-mailed surveys administered through our secure study database RedCap. If patients are not able to respond via text messaging or e-mail they will be called by investigative team. Patients will be called by study staff if they miss 3 or more doses in a 1 week period to provide counseling and determine any potential barriers to taking the study medication. Study staff will contact the participants at 3 weeks for a brief assessment of missed doses, to provide adherence counseling, and collect any reported information about adverse events. At this time a condensed bleeding assessment will be performed to assess bleeding events since the beginning of treatment.

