### **Adverse Event Reporting Period**

The study period during which adverse events must be reported is normally defined as the period from the initiation of any study procedures to the end of the study treatment follow-up. For this study, the study treatment follow-up is defined as 30 days following the last administration of study treatment.

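### Perioperative bleeding has no structured, scheduled capture in hospital; non-serious events rest on a general recording duty and a week-3 look-back

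*Combined protocol and SAP*

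**What the plan says.** All references are to the combined protocol and SAP.

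- **Schedule.** Section 7.6 states "Adverse event assessments will be performed according to the following schedule". The one entry beneath it is headed as monitoring after discharge and reads "Adverse events will be assessed at each patient contact (telephone or text-messaged/mailed survey), which will occur weekly while on the study drug". Section 3.5 tracks the safety endpoint through emailed or texted surveys while patients are on drug. Section 3.1 instead places weekly safety calls across the whole six weeks of treatment.
- **Dosing in hospital.** Section 5.1 describes patients as "hospitalized for a period of time (typically 7-14 days) and therefore will start the study drug immediately after enrollment questionnaire has been completed", with daily dosing through the stay. Planned surgical management is inclusion criterion 4 in section 3.6.
- **Chart extraction.** Section 5.3 opens with a broad statement about how the patient fared and was treated in hospital. On the operation it then says "Data collected regarding the surgical procedure will include donor site location, size, mesh ratio, mechanism of grafting", followed by graft location and surgery date.
- **Bleeding tool.** At the three-week staff contact in section 5.4, a "condensed bleeding assessment will be performed to assess bleeding events since the beginning of treatment". Section 5.5 repeats it at week 6 for the interval since week 3.
- **General safeguards.** The reporting window is "the period from the initiation of any study procedures to the end of the study treatment follow-up". Section 7.2 requires adverse events to be sought at every contact and all of them recorded. Section 7.6 adds "Serious adverse events (SAE's) will be monitored by the study site investigative teams in real time throughout the trial", and section 7.3.1 gives 24 hours for reporting any serious event to the sponsor.
- **Form and exemption.** Section 7.6 calls for the electronic adverse event form for *unanticipated* events. Section 7.1 lists, among circumstances not reported as adverse events, "Hospitalization or prolonged hospitalization for therapy of the target disease of the study", unless the investigator judges it a worsening.

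**The concern.** The protocol treats bleeding as a real fish oil hazard. Section 1.5 lists it as a side effect, section 3.7 excludes patients on named anticoagulant or antiplatelet drugs and those with bleeding disorders, and the adverse event table in section 14.1 has rows for bruising and hematoma. The graft operation is an obvious occasion for that hazard to show itself, yet the structured instruments are outpatient surveys and a retrospective questionnaire. A patient is a poor source for intraoperative blood loss, a transfusion given under anesthesia, or the reason for a second trip to theatre.

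Safety is a primary objective (section 2). Under section 6.2 the safety result is a tabulation by arm with no inferential comparison. With no test or interval to signal imprecision, the completeness of ascertainment largely decides what the table appears to say, and a thin bleeding row could be read as reassurance when planning the larger trial.

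**Working it through.** The plan gives no figure on this point to reproduce. The check compares the text and does simple arithmetic on the plan's own durations.

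**1. What covers an in-hospital bleed?**

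| Source | Serious bleed | Non-serious bleed |
|---|---|---|
| 7.6 schedule entry | headed post-discharge | headed post-discharge |
| 7.6 site monitoring, 7.3.1 reporting | covered | not covered |
| 7.1 reporting window, 7.2 recording duty | covered in principle | covered in principle, no scheduled inpatient assessment |
| 5.3 named extraction items | no bleeding-related item | no bleeding-related item |
| 5.4 week-3 bleeding tool | look-back | look-back |

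Serious events therefore have a prospective route that does not depend on recall. Non-serious events have only the general duty and the look-back.

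**2. Do the recording rules agree?** Section 7.2 requires every adverse event in the study period to be recorded. Section 7.6 requires the electronic form for *unanticipated* events and defines *expected* events as known effects of the drug or disease. Bleeding after burn surgery on fish oil can be read as either kind of known effect, so one rule records it and the other may not trigger the form.

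**3. Do the timing statements agree?** Section 3.1 has weekly calls throughout treatment, section 3.5 surveys during treatment, section 7.6 a post-discharge heading over text that says weekly on drug, and section 4.5 weekly compliance and pain surveys following the treatment period. They do not fix when assessment starts.

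**4. How much exposure is inpatient?** Course length from section 4.4: 168/4 = 42 days for fish oil and 42/1 = 42 days for vitamin D. The typical stay L is 7 to 14 days (section 5.1). Let d be the days of stay before the first dose. The documents do not give d. I take 0, and also 3 or 4 on the assumption that the stay is counted from the burn and dosing begins at the 72-hour (sections 3.1 and 5.1) or 96-hour (section 3.6) limit. Inpatient share = (L − d)/42:

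| d | L = 7 | L = 14 |
|---|---|---|
| 0 | 7/42 = 16.7% | 14/42 = 33.3% |
| 3 | 4/42 = 9.5% | 11/42 = 26.2% |
| 4 | 3/42 = 7.1% | 10/42 = 23.8% |

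The range is about 7% to 33%.

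**5. How long is the look-back?** Week 3 is day 21. With the stay counted from the first dose, the bleeding tool comes 21 − 14 = 7 to 21 − 7 = 14 days after discharge.

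**6. What does one missed event do to the table?** Section 6.2 says the study ended early after the 24th patient. Assuming even allocation, n-3 PUFA versus control is 24/2 = 12 against 12, so one event moves an observed rate by 1/12 = 8.3 percentage points. At the planned 30 per side it would be 1/30 = 3.3 points.

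**7. Which way does under-capture push?** If a fraction s of events is captured in both groups, with true rates p1 and p0, the expected observed difference is s(p1 − p0). Counts fall in all arms and the difference shrinks towards zero; the ratio is unchanged in expectation but rests on fewer events.

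**The case against.** The strongest reply is that the stay is not unmonitored. A reader might infer from section 7.6 that nothing beyond patient recall operates in hospital. The documents do not support that: the reporting window opens with the first study procedure, section 7.2 requires questioning and, where appropriate, examination, and serious events are monitored as they occur and reported within 24 hours. This stands, and limits the point to structured capture of non-serious bleeding.

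Several further objections stand in part.

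- The lists in section 5.3 are not stated to be exhaustive, and the opening wording is broad. That is fair, but an unnamed field is likely to be abstracted differently across sites.
- A reader might infer that bleeding would be under-reported specifically in the fish oil arms. The trial is double-blind (sections 4.3 and 4.8), so the natural expectation is loss in all arms.
- A reader might assume that most operations take place on drug. No section orders surgery after the first dose; the surgery date is collected but not tied to dosing.
- The exemption for treatment of the target disease carries its own exception for worsening, and the default in section 7.1 is that an adverse event prolonging hospital stay is serious. Whether graft-site bleeding falls inside the exemption is open to interpretation.
- A table interrupts the section 7.6 text in the copy reviewed, so a lost inpatient entry cannot be excluded. Nothing shows that one existed, and the original should be checked.

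**Conclusion.** The narrower point holds. The plan has no structured, scheduled inpatient capture of perioperative bleeding, although dosing starts in hospital and bleeding is a named risk. Non-serious in-hospital bleeding depends on a general duty, on an electronic form whose trigger conflicts with that duty, and on recall at week 3. The by-arm table may under-count bleeding in all arms and be less able to show a fish oil difference.

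The exposed period is about 7% to 33% of the course, resting on the assumed start of dosing within the stay. The number of events missed cannot be estimated from the documents. The 8.3-point sensitivity to a single event assumes even allocation of 24 patients. This is an inexpensive improvement to a primary outcome, not a finding that the safety plan fails.

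**What to change.** **Add fields to the section 5.3 extraction:** red-cell transfusion, hematoma or its evacuation, unplanned return to surgery, and graft loss, each dated relative to the first dose. Dating separates events before dosing from those on drug. Abstractors should remain blind to allocation. Tabulate the results by n-3 PUFA versus control, alongside the four-arm table in section 6.2.

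**Reconcile the text:**

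- Sections 3.1, 3.5 and 7.6 on when adverse event assessment starts, with section 4.5 aligned on the weekly surveys.
- Sections 7.2 and 7.6 on which adverse events are recorded and on what form.
- The serious-event definitions in sections 7.1 and 7.6 and the hospitalization exemption in section 7.1, on how a stay prolonged by bleeding is classified. Which rule applies is for the sponsor and investigators to settle.

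**Cost.** Enrollment has ended, so the added fields mean going back to charts already abstracted, for about 24 patients. A prospective inpatient schedule would come too late for these patients but could carry into the larger trial. The medication record should not be relied on to explain doses withheld by staff, because section 4.5 documents reasons for refusal only. More events reflecting the burn itself will be recorded; the randomized control group puts them in context.
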